### **Recruitment Methods**

Participants are recruited from MyChart patient records, screen in Computerized Patient Record System (CPRS), that meet inclusion criteria. Also, to be used: Research Match and social media recruitment via advertisement on relevant pages associated to CPBH, i.e., Memory and Aging Center.

Keywords checked in medical records:

- Mild Cognitive Impairment
- Age 65 or older
- History of Insomnia
- (Add final ICD-10 terms)

### **Reasons for Participant Withdrawal or Termination**

Participants can decide to stop at any time. The study doctor may stop participants from taking part in this study at any time if the doctor believes it is in the participant's best interest, if the participant does not follow study rules, or if the study is stopped

## Study Schedule & Procedure Summary

### SCHEDULE OF EVALUATIONS

ASSESSMENT	Recruitment Pre-screening & Consent	Screening/ Assessment	Baseline Measures/ Start of Trial	9 Weeks/ End of Trial Follow-up
Inclusion/Exclusion Criteria	X			
Medical History	X	X		
Insomnia Severity Index	X	X		X
Pittsburg Sleep Quality Index		X		X
SF-36			X	X
Epworth Sleepiness Scale			X	X
Quality of Life			X	X
Cognitive function			X	X
Geriatric Depression Scale			X	
24-h Actigraphy (3 days)			X	X
Cognitive Assessment Battery			X	X

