## B. FOLLOW-UP MEASURES

Once intervention is completed,

- Feedback at the end of trial via survey and phone follow-up (if needed)
- Follow-up (3-day actigraphy & questionnaires + Cognitive Assessments)
- Follow-up at 24 weeks:
- Final follow-up actigraphy watch measurement
- Follow-up of cognitive assessment + questionnaires

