Official title: Napping, Sleep, Cognitive Decline and Risk of Alzheimer's Disease

NCT#: NCT03256539

Document date: 09/21/2023

SleepTIGHT Statistical Analysis Plan

(Sleep Therapeutics Intervention to improve coGnitive HealTh)

***Full Study Title: Napping, Sleep, Cognitive Decline and Risk of
Alzheimer's Disease***

Principal Investigator: [name]

University of California, San Francisco

[name]

[name]

[contact]

Sponsor

National Institutes of Health

STUDY AIMS

The overall objective is to develop a CBT-I program for people with MCI/ mild Alzheimer's disease and sleep disturbances, pilot test its feasibility, and elucidate its preliminary effects on sleep, cognition and quality of life, with the ultimate aim of decreasing risk of Alzheimer's onset or progression.

Aim 1: To develop a CBT-I program and test its feasibility and acceptability in patients with MCI/ mild Alzheimer's disease and sleep disturbances.

Aim 2: To elucidate the effects of the CBT-I program on patients' subjective and objective sleep quality.

Exploratory Aim: To collect pilot data and explore preliminary effects of 1) the CBT-I program on cognition and quality of life and 2) involving caregivers in the program.

PROCEDURES

We plan to study older adults (aged 65 and above) with MCI or mild AD. Patients will be identified from a combination of online sources, including the UCSF CTSI Electronic Health Record services (MyChart), Researchmatch.org and social media postings, as well as the UCSF Memory and Aging Center (MAC, Director: [name], co-founders include [name]). *The attached figure* outlines the study visits and related measurements.

1. Baseline screening/ Randomization

When a potential participant is identified or expresses interest in the study, study staff will contact them to explain study procedures and go through the key points of the consent form. Once consented, study staff will administer clinical interviews via zoom to assess insomnia, medical history, mood and QDRS-derived global CDR to determine eligibility and obtain visual proof of written informed consent. Eligible participants who consent will be scheduled for a baseline assessment via zoom within 2 weeks of enrollment. The measures described above will also serve as part of the baseline measures.

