For Aim 2 and the Exploratory Aim, we will use t-tests, Wilcoxon or chi-square tests to compare between the treatment and non-treatment groups the change scores in: 1) circadian rhythms parameters (e.g. amplitude, and overall rhythmicity); 2) frequency and length of day naps; 3) quality of nocturnal sleep (e.g. change in ISI scores; increased sleep duration and efficiency; decreased sleep onset time); 4) reported quality of life (SF-36 scores); 5) cognitive scores. Standardized measures of cognitive performance (z-scores) will be calculated for each participant for each neuropsychological test in the battery. Repeated measures models will be used to examine longitudinal treatment effects. These models will include subject-specific (i.e. intercept term) and fixed effects (treatment group, time and the time*treatment interaction). A significant time*treatment interaction will indicate that changes in outcome measures over time are different in the treatment arms. In order to explore the impact of involvement of caregivers, we will repeat the above analysis between the treatment group with and without involvement of the caregiver. The resulting estimates will be imprecise, and thus useful for trial planning only in combination with external data, expert opinion, and established norms for clinically meaningful effects.

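### Actigraphy covers only three unspecified days per recording at baseline and end of trial, which adds avoidable noise, including weekday/weekend mismatch, to the objective sleep change scores

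*Protocol*

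**What the plan says.** Protocol, Schedule of Evaluations: the table lists "24-h Actigraphy (3 days" at baseline and at the 9-week visit.

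Protocol, B. Follow-up Measures: the end-of-trial entry is "Follow-up (3-day actigraphy & questionnaires + Cognitive Assessments". The 24-week entry is "Final follow-up actigraphy watch measurement", with no number of days, and the Schedule of Evaluations has no 24-week column.

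SAP, Study Aims: Aim 2 is "To elucidate the effects of the CBT-I program on patients' subjective and objective sleep quality". The watch supplies the objective part.

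SAP, Statistical Analyses: "we will use t-tests, Wilcoxon or chi-square tests to compare between the treatment and non-treatment groups the change scores in" a list that begins with "circadian rhythms parameters (e.g. amplitude, and overall rhythmicity" and "frequency and length of day naps" and goes on to nocturnal sleep duration, efficiency and onset. The SAP does not state a recording length.

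SAP, Baseline Visit: a diary accompanies the watch and records naps and watch removal. This helps scoring but does not lengthen or balance the recording.

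Neither document gives a reason for three days, fixes a start day, asks for the same weekdays at each visit, says how many days make a usable recording, or adjusts for day type.

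**The concern.** Three consecutive days cannot span a week. Whether a recording includes a weekend depends on the day it starts, and nothing keeps that constant from one visit to the next. If a participant naps or keeps hours differently at weekends, part of the measured change reflects the calendar. Separately, a summary over three days carries more day-to-day variation than one over seven, and a change score carries that variation twice.

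What is at stake is the precision of the objective sleep results in Aim 2. With 40 participants that precision is already limited, and longer wear of the same watch is a cheap way to improve it. One lost day also matters more in a recording of three (two left) than in one of seven (six left).

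**Working it through.** The documents give no power calculation, standard deviation, reliability or target precision for actigraphy, so there is no figure of the plan's own to reproduce. Two checks follow. The first is a count and needs one assumption about scheduling. The second depends on assumed reliabilities.

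**1. Weekend days in a three-day window**

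Input: three consecutive days (Protocol, Schedule of Evaluations and B. Follow-up Measures; that the days are consecutive is assumed).

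- Start Monday to Sunday: 0, 0, 0, 1, 2, 2, 1 weekend days. Three starts give none, two give one, two give two.
- If baseline and follow-up start days are independent and uniform over the week, P(same count) = (3² + 2² + 2²)/49 = 17/49, so P(different) = 32/49 = 65%.
- Variance of the count = 10/7 − (6/7)² = 34/49. Variance of the weekend share = (34/49)/9 = 0.077. SD of the change in share = √(2 × 0.077) = 0.39. The largest possible shift is 2/3.
- A complete seven-day window always holds two weekend days, so the mismatch is 0%. Three-day windows that start on the same weekday also give 0%.

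**2. Day-to-day noise, for outcomes that are averages of daily values**

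Assumptions, not in the documents: single-day reliability (ICC) 0.2 to 0.7; true between-visit correlation r of 0.5 or 0.8; seven days as comparator. One-day variance is scaled to 1.

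- Reliability of a k-day mean: R = k·ICC / (1 + (k − 1)·ICC)
- Change-score variance: V = 2·ICC·(1 − r) + 2·(1 − ICC)/k

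| ICC | R, 3 days | R, 7 days | r | V, 3 days | V, 7 days | Cut in variance | SD ratio, 3 vs 7 |
|---|---|---|---|---|---|---|---|
| 0.2 | 0.43 | 0.64 | 0.5 | 0.733 | 0.429 | 42% | 1.31 |
| 0.2 | 0.43 | 0.64 | 0.8 | 0.613 | 0.309 | 50% | 1.41 |
| 0.5 | 0.75 | 0.88 | 0.5 | 0.833 | 0.643 | 23% | 1.14 |
| 0.5 | 0.75 | 0.88 | 0.8 | 0.533 | 0.343 | 36% | 1.25 |
| 0.7 | 0.87 | 0.94 | 0.5 | 0.900 | 0.786 | 13% | 1.07 |
| 0.7 | 0.87 | 0.94 | 0.8 | 0.480 | 0.366 | 24% | 1.15 |

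**3. What that means for 40 participants**

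Further assumptions: 20 per arm (the allocation ratio is not stated), two-sided alpha 0.05, no dropout, normal approximation.

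- Effect detectable with 80% power: (1.960 + 0.842) × √(2/20) = 0.89 SD of the change score.
- For an illustrative effect of 0.8 SD on the seven-day scale, power = Φ(0.8 × √10 − 1.96) = 72% with seven days. Dividing 0.8 by the SD ratios 1.41 and 1.07 gives 43% and 66% with three days.
- Participants per arm for 80% power at that effect: 25 with seven days, 29 to 49 with three.

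**The case against.** Several objections are fair, and most of them limit the point.

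*Three days is not shown to be inadequate.* A reader might infer that the recording is simply too short. The documents do not support that: they give no reliability or target precision against which three days fails. The loss is a matter of degree, from modest (13%) to large (50%).

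*The averaging formula does not fit every outcome.* Overall rhythmicity describes a pattern across the whole record, and the SAP does not say how it or amplitude is computed. The figures suit nap frequency or sleep duration better than rhythmicity indices. For the latter the direction is plausible, but the size is not established here.

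*The 65% is a scenario.* Nine and 24 weeks are whole weeks, so follow-up booked exactly on those anniversaries would match the baseline weekday. Neither document requires this. The size of any weekday/weekend difference at age 65 and over, with shift workers excluded, is also unknown.

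*Randomisation protects the comparison.* A reader might infer that mixed day types bias the treatment effect. They do not, unless scheduling differs by arm, and nothing in the documents suggests that. The mismatch is extra variance in both arms.

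*This is a feasibility pilot.* Feasibility is the primary goal, and the SAP itself concedes that its estimates will be imprecise. That lowers the priority. It does not remove the gain, because Aim 2 has planned between-arm tests and the estimates are meant to inform later planning.

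*Longer wear has a cost here.* Adherence, missing data and burden are themselves feasibility and acceptability outcomes, in people with MCI assessed remotely. This stands and must be weighed in the fix.

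**Conclusion.** The point holds as an improvement of moderate priority. It is certain that three days cannot represent a full week and that no rule aligns the days between visits. The 65% mismatch rests on unaligned, evenly spread start days and measures added noise only. The 13% to 50% cut in change-score variance from seven days rests on the assumed ICC and correlation ranges and applies to daily averages with complete wear. The power figures also rest on equal allocation and the illustrative effect. At week 24 the recording length is simply unstated, so nothing can be said about its adequacy. No feasibility conclusion is affected.

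**What to change.** In the Schedule of Evaluations and in B. Follow-up Measures, replace three days with seven consecutive days at baseline, week 9 and week 24, and start each recording for a participant on the same weekday. State the recording length in the SAP as well.

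In the SAP, analyse all valid days and include a weekday/weekend term, since incomplete wear can unbalance day types even in a seven-day recording. Define a valid day, but do not exclude participants who fall below a minimum number; report completeness as a feasibility outcome. An exclusion rule could remove people from an intent-to-treat sample of 40. A participant at a four-day minimum would also gain little. With r = 0.7, change-score variance goes from 0.633 to 0.550 at ICC 0.5 (13%) and from 0.647 to 0.530 at ICC 0.3 (18%).

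Cost: four more days of watch and diary wear per recording in participants with MCI, and slower watch turnaround. The device is the same and no visit is added. Timing needs a check: the Protocol allows 10 to 13 weeks from screening to post-study assessment around a 9-week programme. That leaves 1 to 4 weeks, and two seven-day recordings take 2 weeks unless the second overlaps the end of the programme.

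If the burden is judged too high, keep three days and match the weekdays across visits. With complete wear this removes the mismatch at almost no cost, but it leaves the three-day noise and the incomplete coverage of the week.

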### INITIAL CONTACT AND SCREENING

1. Participants, after being identified or reaching out to research team with interest, will be called with initial **contact phone script**, given introductory information about the study, asked to confirm their interest and given the option to fill **consent form** on same call or to schedule follow-up call for consent. IF participant is still interested, consent form is signed, then **ISI questionnaire** is given.

2. Followed by appointment for:

- Baseline Cognitive Assessment Interview: 1 hour via Zoom.
- Administer the following questionnaires:
  - **Pittsburg Sleep quality index**
  - **Epworth Sleepiness Scale**
  - **36-item short-form survey**

### If continued interest, eligible, and consented

- Schedule meeting for briefing via Zoom on Somryst program or placebo condition materials
- Intervention **or** attention-matched placebo program (6 weeks) + Weekly meetings with research team for clarification or assistance with materials and content

## A. INTERVENTION

Over six weeks, the research team will have scheduled meetings with participants to deliver content and instructions for use of the Somryst

The Somryst program is intended to deliver 6 treatment Cores, with the following specific CBT-I therapy content:

1. **Get Ready:** This Core sets the stage for the therapeutic experience. It lets the participant know what they will need to learn and do to improve sleep and sets goals for success.
2. **Sleep Window:** This Core focuses on the concept of sleep restriction and identifies a Sleep Window - a recommended Bedtime and Arising Time – the participant should follow.
3. **Behaviors:** This Core focuses on stimulus control and establishes guidelines for participants to follow while implementing their Sleep Window.
4. **Thoughts:** This Core explains how a participant's thinking can contribute to insomnia. The participant will learn to identify, and shift thought patterns.
5. **Education:** This Core helps the participant identify changes to be made in their lifestyle and environment that can promote better sleep.
6. **Looking Ahead:** This Core pulls together what the participant has learned, prepares the participant for the future, and teaches them what to do if they experience a relapse. Somryst also includes a daily Sleep Diary in which the participant records information about their sleep.

## B. FOLLOW-UP MEASURES

Once intervention is completed,

- Feedback at the end of trial via survey and phone follow-up (if needed)
- Follow-up (3-day actigraphy & questionnaires + Cognitive Assessments)
- Follow-up at 24 weeks:
- Final follow-up actigraphy watch measurement
- Follow-up of cognitive assessment + questionnaires

## OUTCOME MEASURES

Primary Outcomes

### Feasibility

Proportion of eligible participants consented

- Proportion of participants randomized after baseline assessment
- Number of CBT-I sessions completed
- Adherence/compliance rates
- Follow-up rates
- Missing data (data completeness)
- Time needed to collect and analyze data

### Acceptability

General study satisfaction

Acceptability of intervention

Barriers & Burden

[figure not shown]
Qualitative interview

## Data Collection and Storage

Patient information is collected and stored in REDCap.

Once assessments are completed, they will be scored and recorded for later analysis.

## Study Outline Graphic

**Figure 1 Outline of study visits and related measurements**

## APPENDIX A.

### SLEEPSIGHT INITIAL CONTACT TELEPHONE SCREENER

#### Full study title - Napping, Sleep, Cognitive Decline and Risk of Alzheimer's Disease

##### (For those who were pre-screened)

\_\_\_\_\_ Hello, my name is \_\_\_\_\_ and I am calling about a research study called SleepTIGHT being conducted at UCSF by Principal Investigator [name].

Is this a good time? Do you have time to talk for about five to seven minutes to learn briefly about our research study?

If no: what would be a good time to call you? (Specify follow-up) \_\_\_\_\_

If yes: Great! Broadly speaking, this research study is about digital therapeutics to treat sleep problems and improve cognition ([Go to BRIEF STUDY OVERVIEW](#)).

##### **[For calling back individuals who asked for more information]**

Hello, my name is \_\_\_\_\_. Thanks for expressing interest in our research study about sleep, insomnia, and cognitive decline. We appreciate you calling to learn more. The study is being conducted by researchers at the Department of Psychiatry and Behavioral Sciences at UCSF. We wanted to call today to tell you more about the study. Is this a good time? Do you have time to talk for about five to seven minutes to learn briefly about the study?

##### **BRIEF STUDY OVERVIEW**

Next, I'm going to give you a description of the study. Please stop me if you have any questions.

As mentioned earlier, SleepTIGHT is a study using a digital therapeutic treatment for improving sleep patterns in people with mild impairment in mental processing. This study is unique in that it requires no in-person visits, and the therapy is FDA-approved.

Participants will meet with researchers via phone and videoconference and undergo 6 weeks of (approx. 1 hour) sessions. You will be keeping a sleep diary to track progress and describe sleeping patterns over the course of the study. You will also complete questionnaires that ask about your experience in the program, your quality of life, sleeping habits and mental processing.

The primary goals with treatment are to improve sleep habits which may benefit your mental processing and slow or prevent risk for cognitive decline.

If you are interested in enrolling, you will take part in a few questionnaires and cognitive tests. These are necessary to make sure you are eligible to participate. The screening questions will ask about your quality of life, overall health, mood, and sleep. We also will ask about cognitive function. These questionnaires will take about 45 min – 1 hr. for you to complete.

After this, if you are interested and potentially eligible based on the screening, we will schedule a second appointment via videoconferencing to confirm your eligibility and complete necessary paperwork to begin the study.

Are you still interested in participating? Do you have any questions?

Would you like to do an initial screening for the study, or should I call back later? (it should take an additional 10-15 minutes)

**\*\*\*Please note that you are free not to answer any questions you are uncomfortable with, and otherwise please answer as accurately as possible (to best determine your eligibility).**

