### Description of the Intervention

We will randomize patients, using computer-generated random numbers, to one of two treatment arms:

- a) an FDA-authorized prescription digital CBT-I therapeutic treatment
- or
- b) an interactive, attention-matched, internet-based placebo control program.

At the beginning of the intervention, study staff will give instructions on the use of the programs via zoom.

Throughout the intervention, study staff will call the participants weekly to give further clarifications and answer questions. Somryst is a 9-week program that delivers digital CBT-I therapeutic content, and can be used on a mobile device, such as a smartphone or tablet. CBT-I is a neurobehavioral treatment which focuses on addressing the maladaptive behaviors, routines, and dysfunctional thoughts that perpetuate sleep problems, regardless of the cause of sleep problems. CBT-I can be conceptualized as six sessions or cores that deliver proven behavioral and cognitive treatment strategies.

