### Potential Benefits and Risks to Participants

There will be no direct benefit to the participants from taking part in this study. Taking part in this study may or may not make their health better. While doctors hope that cognitive training therapies will be beneficial, these trainings are still being studied.

Some of the most likely risks of participation in this study include:

- Risk of fatigue/distress: Finding study activities difficult, tiring, time-consuming, anxiety-provoking, frustrating, or boring. Participants are free to decline to answer any questions or to stop at any time. To reduce fatigue, breaks are scheduled during testing and training sessions. Additional breaks will be provided at the participant's request. If the participant appears to be under undue strain, the session will be discontinued.
- Risk of loss of privacy: Participation in research may involve a loss of privacy. Because training takes place in a small group setting, other research subjects within the group may become aware of information that participants would prefer to not be shared outside of the group. Researchers will ask all subjects to keep private all information learned about other group members and to not talk about this information outside of group sessions. However, absolute confidentiality cannot be guaranteed. The researchers will keep information about participants as confidential as possible, but complete confidentiality cannot be guaranteed. On rare occasions, a court has subpoenaed research records. Other University of California personnel may also review or receive information about the participants. Study PI and research staff will retain the participant's research records indefinitely for research purposes. Personal identifiable information (PII) and protected health information (PHI) cannot be used for additional research without additional approval from either the participant or a review committee.
- Unknown risks: The experimental treatments may have risks or side effects that no one knows about yet. Members of the research team will inform participants about any new information that may impact their decision to remain in the study.

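### The recruitment scripts present one FDA-approved therapy and omit random assignment and the placebo program; with no participant blinding or arm-guess item described, expectation could come to differ by arm without being detected

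*Protocol*

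**What the plan says.** The Brief Study Overview in Protocol Appendix A introduces the study with "SleepTIGHT is a study using a digital therapeutic treatment for improving sleep patterns in people with mild impairment in mental processing" and continues: "This study is unique in that it requires no in-person visits, and the therapy is FDA-approved". It describes one course for everyone: "Participants will meet with researchers via phone and videoconference and undergo 6 weeks of (approx. 1 hour) sessions". It gives the purpose as: "The primary goals with treatment are to improve sleep habits which may benefit your mental processing and slow or prevent risk for cognitive decline".

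The Protocol's Description of the Intervention gives a different design: "We will randomize patients, using computer-generated random numbers, to one of two treatment arms". Arm (a) is "an FDA-authorized prescription digital CBT-I therapeutic treatment"; arm (b) is "an interactive, attention-matched, internet-based placebo control program". The SAP (Procedures, item 2) says the same and also applies the FDA term to arm (a) only. Under Potential Benefits and Risks to Participants the Protocol states: "There will be no direct benefit to the participants from taking part in this study". It then adds that participants' health may or may not improve.

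Neither the rest of Appendix A nor the Appendix B phone screening script mentions randomization, chance, a placebo or a control program. The Informed Consent Review list has an entry for study procedures but does not name randomization or placebo. The consent form is not in the supplied file.

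**The concern.** A candidate who hears only the script would reasonably picture a single-arm study of an approved treatment. That conflicts with the design and needs correcting whatever its effect on the results.

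The statistical interest lies in what may follow. The ISI, PSQI, Epworth scale, SF-36 and satisfaction ratings are all self-reported, and willingness to stay in the study also responds to expectation. An attention-matched control is meant to keep such influences equal between arms. If control participants realise that their program is not the therapy described on the phone, disappointment could worsen their scores, adherence and retention, and so flatter the CBT-I arm. Without a question on what participants believe they received, the report could not say whether the control did its job.

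**Working it through.** The documents give no figure on this point to reproduce, so the main check is textual.

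**Script against design**

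1. *Number of arms.* The script has one therapeutic and one course of sessions. Description of the Intervention and SAP Procedures item 2 have two randomized arms. The script leaves out the control arm.
2. *Regulatory status.* The script calls the therapy approved, with no arm attached. The design sections say authorized, for arm (a) only. The Protocol gives 40 subjects and no allocation ratio. If the ratio is 1:1 (assumption), 40 / 2 = 20 people receive a program to which the statement does not apply.
3. *Benefit.* The script offers sleep and cognitive goals of treatment. The benefits section promises no direct benefit. The script is hedged, so this is a difference of emphasis rather than a flat contradiction.
4. *Order.* Initial Contact and Screening places the introductory call before the consent form. Randomization comes later still. The script therefore reaches people who will be in either arm, before anyone is allocated.

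**What a between-arm difference would require**

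- *The script raises expectation.* Plausible from its wording, but equally so in both arms, by item 4.
- *Control participants later recognise their arm.* This depends on the consent form, the Zoom briefing and the control content. The first is not supplied. For the second, the Protocol says only that staff brief on the product or on the placebo materials, and does not give the words used. For the third, only the short description of arm (b) is given.
- *Outcomes respond to belief.* Credible for the self-reported measures in SAP section 3, Follow-up and outcome measures.
- *A safeguard or a check.* The supplied text describes neither participant blinding nor an arm-guess or expectancy item.

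Only the second link produces a difference between arms, and it cannot be established from the documents.

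**Illustration of size, on assumptions only**

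Assume 20 per arm, a two-sided 5% t-test on change scores and no true effect. Let expectation shift the control mean by d standard deviations. The SAP names t-tests among its methods but gives no significance level or standard deviation. With n per arm, the noncentrality is d × √(n/2) = d × √10 = 3.162d, on 2 × 20 − 2 = 38 degrees of freedom. The probability of rejecting is then:

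- d = 0: 5%
- d = 0.2 (noncentrality 0.632): 9.5%
- d = 0.3 (noncentrality 0.949): 15.2%
- d = 0.5 (noncentrality 1.581): 33.8%

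The values of d are chosen, not estimated. The list shows that a modest shift could matter at this sample size; it is not evidence that a shift occurs.

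**The case against.** The strongest reply is that a reader might infer more than the text supports. Several stronger readings do not stand:

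- *Each candidate is told that they will receive the therapy.* The script implies this but never says it. Its statement describes a product and does not become false through a person's allocation.
- *Control participants will notice that a named product is missing.* The phone scripts name no product. Appendix B already refers to the study's own program and material in neutral terms.
- *Control participants can work out their arm, so expectation does differ.* The script is read before allocation and by itself acts equally on both arms. The Protocol's mention of placebo materials is a procedural line for staff; nothing shows that participants hear the word. Consent precedes the study's ISI and baseline assessment in Initial Contact and Screening, and may explain randomization.
- *The feasibility rates are distorted.* If people decline when consent explains the placebo, the proportion consenting records the behaviour it is meant to measure. That part of the worry largely falls away.

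Two further limits are fair. The between-arm comparisons belong to Aim 2 and the Exploratory Aim, and the SAP itself says that the estimates will be imprecise and useful for planning only alongside other information. The end-of-trial survey is not reproduced, so a belief item cannot be wholly excluded.

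What remains is the confirmed mismatch between scripts and design, together with the absence from the supplied text of any participant blinding or any check of belief.

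**Conclusion.** The scripts should be corrected. It is established that they present one therapy with an unqualified FDA claim and treatment goals, and omit random assignment and the control program. This disagrees with the design in both documents and fits poorly with the Protocol's benefits section.

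A resulting difference between arms in self-reported outcomes, satisfaction or retention is plausible but not shown. It rests on control participants recognising their program after allocation, which turns on consent, briefing and control content that cannot be seen here. No size can be derived from the documents; the rejection rates above follow wholly from assumed shifts, an assumed 1:1 allocation and an assumed 5% level. The consequence is further limited because the primary outcomes are feasibility and acceptability and the effect comparisons are preliminary. The point merits action mainly because the script is wrong as it stands and the remedy is inexpensive.

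**What to change.** 1. In the Appendix A overview, say that the study compares two online programs, that participants are assigned to one of them by chance, that one is a control, and that it is not known whether either helps sleep or thinking.
2. Delete the unqualified FDA statement and the treatment-goals sentence. If regulatory status is mentioned anywhere else to candidates, use the Protocol's term and say that it applies to one program only.
3. Use one neutral program name for both arms in the Zoom briefings and weekly calls.
4. Add one item to the end-of-trial survey already planned under Follow-up Measures: *Which program do you think you had, and why?* Report the answers by arm beside the ISI and satisfaction results.

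The cost is a change to the script and IRB wording, one survey item, and slightly less persuasive recruitment. Saying that one program is a control may prompt some guessing, and the product name may still be visible inside the app. Neutral wording cannot remove either, which is why the belief item is needed.
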